8.2 Clinical Assessments

8.2.1 Demographics

Demographic information (date of birth, gender, race) will be recorded at Screening.

8.2.2 Medical History and ALL Disease History

Relevant medical history, including history of current disease and information regarding underlying diseases, will be recorded at Screening and from the NOPHO database.

8.2.3 Physical Examination and Vital Signs

A complete physical examination will be performed by either the investigator or a sub-investigator who is a physician at Screening, during Course Evaluation and at the End of Study Visit. Qualified staff may complete the abbreviated physical exam at all other visits. New abnormal physical exam findings must be documented and will be followed by a physician or other qualified staff at the next scheduled visit.

- Full physical examination including height (at baseline only), weight and vital signs (body temperature, blood pressure and pulse rate)
- Karnofsky/Lansky score performance status.

8.2.4 ALL Clinical Assessment

ALL clinical assessment will be performed at Screening, and at the end of the study.

8.2.5 Adverse Events/Serious Adverse Events Assessment

See Section 10.0 "ADVERSE EVENT REPORTING AND DOCUMENTATION."

8.3 Clinical Laboratory Measurements

Performed as standard of care.

8.3.1 Biological safety parameters

Before initiating therapy, bilirubin, hepatic transaminases, and coagulation parameters (e.g., partial thromboplastin time (PTT), prothrombin time (PT), antithrombin III and fibrinogen) should be determined.

After administration of eryaspase, monitoring of bilirubin, hepatic transaminases, urinary glucose, coagulation parameters (e.g., PTT, PT, anti-thrombin III, fibrinogen, and D-dimer), amylase, lipase, triglycerides, and cholesterol is recommended. Plasma glucose must be measured regularly if the patient has concomitant treatment corticosteroids and if the urine shows sign of glucose and managed as clinically indicated.

In 2 weeks courses, baseline sampling (before administration) is used as a control after the preceding administration. In 6 weeks courses, parameters will be determined at least once in the treatment period.

Additional blood counts can be performed due to clinical conditions and as standard of care.

8.3.2 Maintenance Metabolites

Maintenance metabolites will be measured once a month during first year of maintenance. Blood samples will be collected at local institutions and sent to: The Laboratory for Pediatric Oncology, Bonkolab 5704, The National University Hospital, Rigshospitalet, Copenhagen, Denmark. Here it will be stored and analysed.

Hematological parametres (Hemoglobin, thrombocytes, White Blood Cell Count) and liver parameters (bilirubin, alanine aminotransferase (ALAT), Lactate dehydrogenase (LDH)) have to be measured at the same time points. Furthermore, details about maintenance therapy have to be filled in the CRF.

8.4 Pharmacokinetic/Pharmacodynamic and Immunogenicity Assessments

A laboratory manual describing sample collection, processing and shipment will be provided to investigational center. Blood samples will be collected at local institutions and sent to pediatric research laboratory, Aarhus University Hospital (AUH), Denmark, where it will be stored and analyzed.

Detailed procedures and logistic for the management of samples are detailed in the lab manual provided to the sites.

8.4.1 Total Asparaginase Activity

Blood samples will be drawn to determine asparaginase activity as follows:

Courses with dose every 2 weeks:

- 15 min (\pm 5 min) before eryaspase administration
- End of infusion (0-10 min)
- 24 hours post-infusion (\pm 2 hrs)
- 3 days (\pm 1 day) post-infusion
- 6 days (\pm 1 day) post-infusion
- 10 days (\pm 2 days) post-infusion
- 14 days (\pm 2 days) post-infusion. The 14-day post-infusion sampling corresponds with the pre-eryaspase for next dose (i.e., the Day 15 sample for dose 1 = the pre-dose sample for dose 2, etc.)

Courses with dose every 6 weeks:

- 15 min (\pm 5 min) before eryaspase administration
- End of infusion (0-10 min)
- 24 hours post-infusion (\pm 2 hrs)
- 3 days (\pm 1 day) post-infusion
- 6 days (\pm 1 day post-infusion
- 10 days (\pm 2 days) post-infusion

- 14 days (\pm 2 days) post-infusion
- 21 days (\pm 2 days) post-infusion

8.4.2 Amino acids: asparagine, aspartate, glutamine, and glutamate

8.4.2.1 Amino-acids in CSF

Samples for asparagine, aspartate, glutamine, and glutamate levels in CSF will be drawn when intrathecal therapy occurs according to the time points in the NOPHO ALL 2008 or ALLTogether pilot protocol schedule.

8.4.2.2 Amino-acids in whole blood and plasma

Samples for asparagine, aspartate, glutamine, and glutamate levels in whole blood and plasma will be drawn at the time points for “Total asparaginase activity” according to section 8.4.1. Every effort will be made to collect these samples.

8.4.3 Anti-Asparaginase Antibodies

Anti-asparaginase antibodies will be measured **within 3 days before each eryaspase administration** and at the time points for blood samples for asparaginase activity at the end of the course.

8.5 Blood volumes

The blood volume for each blood count:

- Enzyme activity and asparaginase antibodies: 4mL
- Whole blood and plasma amino acids: 1,2 mL
- Maintenance metabolites: 2 mL
- coagulation parameters: 2 mL
- Hematological parameters: 2 mL
- Liver enzymes, bilirubin, amylase, lipase: 2 mL
- Irregular antibody screening test: 4 mL

Blood volume drawn at individual visit:

- Baseline visit: 11,2 mL
- Visit including measurement of enzyme activity, antibodies, whole blood and plasma amino acids: 5,2 mL
- Visit including biological safety parameters: 6 mL
- Visit including maintenance metabolites: 6 mL

Some of the blood samples will be drawn at the same visit, the maximum blood volume for an individual visit is: 11,2 mL.

Blood volume drawn at each course:

- The maximum total extra blood volume for a 2 weeks course is: 53,2 mL
- The maximum total extra blood volume of a 6 weeks course is: 69,6 mL

The total blood volume for the total duration of the trial would be individual according to the number of doses and courses.

The blood sampling for maintenance metabolites would be measured even if the patient was not included in this study according to the NOPHO protocol. Furthermore, the hematological parameters and Liver enzymes would be performed as standard of care and will not be extra blood counts as well. Both these blood counts are included in the volume above.

The Investigator will contact the Medical Monitor regarding any pediatric patients who require adaptation of the blood sample schedule due to the patient's body weight in consideration of ICH Topic E11 Clinical Investigations of Medicinal Products in the Pediatric Population(26).

8.6 Setting up a Research Biobank

A research biobank will be set up for storing of the samples collected from each study participant for the analysis mentioned in the section above. Peripheral blood for analysis of asparaginase activity and antibody measurements (4 mL per sampling) and CSF (2 mL from each sampling) for analysis of amino acids will be stored at "Pediatric research laboratory", Aarhus University Hospital. Peripheral blood for measurements of maintenance metabolites (2 mL per sampling) will be stored at Bonkolab, Rigshospitalet. The biobank will terminate at 01. January 2021 and excess biological material will be stored for future studies in a biobank established for the purpose at two departments mentioned above. Separate approval from the Committee on Health Research Ethics will be procured, if the material is to be used. Samples will be destroyed in year 2036 at the latest.

9.0 EVALUATIONS BY VISIT

9.1 Screening

Informed consent form will be obtained from the patient prior to any study specific procedures. The screening visit must be performed at the latest 8 days before start of eryaspase treatment. The following assessments and procedures will be performed and documented:

1. Informed consent form signature
2. Check of inclusion and exclusion criteria (to be repeated in case of occurrence of an adverse event)
3. Demographic data (patient initials, date of birth, gender)
4. Risk group according to treatment protocol (NOPHO ALL 2008 or ALLtogether pilot protocol).
5. Physical examination including height, weight and vital signs according to the normal procedure at the centers.
6. Karnofsky/Lansky score
7. ALL clinical assessment according to the normal procedure at the centers.
8. Record all Concomitant Medications

9. Blood phenotype and ABO status

10. IAST Results

The above data will be collected on the relevant page of the CRF.

9.2 Day 1 of each eryaspase administration (± 2 days)

1. Physical examination if clinician finds it necessary.
2. Perform and record vital signs (temperature, blood pressure, pulse rate) and weight.
3. Evaluate Karnofsky/Lansky score
4. Evaluate ALL Clinical Assessment according to the normal procedure at the centers.
5. Record any AEs/SAEs
6. Record any newly added concomitant medications
7. Collect blood for PK/PD testing
8. Collect blood for Antibodies Titers
9. IAST Results within 72 hours prior to each administration
10. Administer eryaspase via IV 150 IU/kg

9.3 Study Termination Visit

30 days after the last administration the patients will enter planned course of treatment and the follow-up program described in the NOPHO ALL 2008 protocol. A separate study termination visit is not required for the patients enrolled in the study.

10.0 ADVERSE EVENT REPORTING AND DOCUMENTATION

Adverse event (AE) are defined as any untoward medical occurrence in the patient after infusion of eryaspase, which does not necessarily have a causal relationship with this treatment. Adverse reactions (AR) are defined as any untoward and unintended response to the investigational medicinal product related to any dose administered.

All AEs must be registered until 30 days after last administration. The Investigator should ensure that adequate medical care is provided to the subject for any adverse event.

If there are several events and different symptoms combined to a main AE, then the only main AE (diagnostic preferable if available) should be recorded in the CRF. Where there is no link between different clinical symptoms occurring at the same time, each sign should be recorded as a separate AE

The following should not be recorded as AEs:

- Pre-planned procedure, unless the condition for which the procedure was planned has worsened from the first trial related activity after the subject has signed the informed consent.
- Pre-existing conditions found as a result of screening procedures.
- Other events, any grade, not related to eryaspase, will not be recorded in the CRF.

If seriousness criterion is met, a SAE should be declared to NOPHO drug safety, completing SAE report form.

10.1 Serious Adverse Events (SAE)

An adverse event is defined as "serious" when at least one the following criterion is met:

- Results in death: be aware that a death cannot be an event but always the outcome of an event. Exception is when death occurs suddenly, without the exact cause is stated. In this case only, the event should be recorded as "sudden death" with the seriousness criterion "fatal" indicated.
- Is life-threatening: life-threatening in the definition of a serious adverse event refers to an event in which the subject was at risk of death at the time of event; it does not refer to an event which hypothetically might have caused death if it was more severe.
- Requires inpatient hospitalization or prolongation of existing hospitalization.
- Results in persistent or significant disability/incapacity.
- Is a congenital anomaly or birth defect.
- Is considered as serious according investigator judgment in other situation. Important adverse events/ reactions that are not immediately life-threatening or do not result in death or hospitalization but may jeopardize the subject or may require intervention to prevent one of the other outcomes listed above, should also be considered serious.

10.2 AEs/SAEs not to be reported

When treating children with cancer, the strategy is generally to treat to the limit of toxicity. Thus, all patients will be at a significant risk of experiencing AE's and SAEs, and all patients and families are informed hereof, when they enter therapy. Most patients will experience febrile neutropenia with or without confirmed bacteraemia, and these are potentially life threatening or may require inpatient hospitalization or prolongation of existing hospitalization. Thus, these AE's and several other SAEs reflect the overall treatment intensity of the current protocols for childhood ALL and not only the

treatment of asparaginase. In addition, treating to neutropenia is in principle the goal of several of the treatment phases and will frequently lead to infections (febrile neutropenia and other infections).

A number of toxicities are so well-known and frequent during therapy that they will not be reported. These includes:

- Since leukopenia is the target toxicity (monitoring parameter), this side-effect will not be regarded as a SAE. This also includes febrile neutropenia leading to hospitalization or prolongation of ongoing hospitalization if the patient's condition otherwise is good with no signs of septic shock.
- Since thrombocytopenia is the target toxicity (monitoring parameter) this side-effect will not be regarded as a SAE.
- A rise in aminotransferases with normal liver function tests (i.e. bilirubin and INR (or coagulation factor 2-7-10) is a well-known side effect of HD-MTX, 6MP and asparaginase and will not be regarded as a SAE.
- A rise in bilirubin to less than 5x UNL.
- Hyperglycemia will not be reported.
- Infection/fever leading to hospitalisation or prolongation of existing hospitalisation.

The overall safety and tolerability of eryaspase in combination with multi-agent NOPHO ALL 2008 or ALLTogether pilot protocol chemotherapy will be evaluated according to the PdL toxicity consensus definitions for asparaginase related toxicities (hypersensitivity, pancreatitis, hyperlipidemia, SOS, thrombosis, osteonecrosis, and fungal infections)(1). Table 3 contains the toxicities potentially related to treatment with asparaginase. All of these toxicities must be reported to PI's and on the CRF.

TABLE 3. POTENTIAL RELATED TOXICITY TO ASPARAGINASE (1)

Toxicity	Consensus definition
Hypersensitivity to asparaginase	An adverse local or general response from exposure to Asparaginase characterised by flushing, rash, urticaria, drug fever, dyspnoea, symptomatic bronchospasm, oedema/angioedema, hypotension and/or anaphylaxis. Grading: 1. Mild: transient flushing or rash, drug fever <38° C, 2. Severe: drug fever >38° C; allergy-related edema/angioedema; dyspnoea and/or symptomatic bronchospasm with or without urticarial; and/or hypotension and anaphylaxis with indication for Asp infusion interruption and parenteral medication (e.g. antihistamines, glucocorticosteroids).
Silent inactivation of asparaginase	No clinical allergy, but trough Asparaginase activity levels below lower level of quantification (preferably measured in two successive independent samples). In case of biweekly PEG-Asparaginase, a day 7 Asparaginase activity level <100 IU/L and/or a day 14 level <LLQ.
Hyperlipidemia	Triglycerides/cholesterol above ULN. Grading: 1. Mild: triglycerides/cholesterol <10 times ULN, 2. Moderate: triglycerides/cholesterol 10-20 times ULN, 3. Severe: triglycerides/cholesterol >20 times ULN. Note: Measurements only as part of research protocols. Dose modification based only on laboratory findings is not recommended.
Osteonecrosis	Osteonecrosis results from the temporary or permanent loss of the blood supply to the bones, which can cause pain, limitation in activity of daily living, and may result in collapse of an articulating surface with enhanced pain and development of arthritis. It should be confirmed by magnetic resonance imaging. Grading: 1. Asymptomatic with findings only by MRI, 2. Symptomatic, not limiting or only slightly limiting self-care ADL. Lesions only outside joint lines in non-weight-bearing bones, 3. Symptomatic, not limiting or only slightly limiting self-care ADL. Lesions in weight-bearing bones or affecting joint lines in non-weight-bearing bones, 4. Symptomatic with deformation by imaging of one or more joints and/or significantly limiting self-care ADL.
Asparaginase-associated pancreatitis	At least two of three features must be fulfilled: i) abdominal pain strongly suggestive of pancreatitis, ii) serum lipase or amylase ≥3 times UNL, iii) characteristic imaging findings of pancreatitis (US/CT/MRI). Re-exposure should only be considered in mild cases. Grading: 1. mild: symptoms and enzyme elevations >3 times ULN that last <72 hours, 2. severe: symptoms and enzyme elevations above >3 times ULN that last ≥72 hours or haemorrhagic pancreatitis or pancreatic abscess or cyst, 3. death from pancreatitis.
Sinusoidal obstruction syndrome	Fulfilment of at least three out of five criteria: i) hepatomegaly, ii) hyperbilirubinaemia >ULN, iii) ascites, iv) weight gain of at least 5%, and v) thrombocytopenia (transfusion-resistant and/or otherwise unexplained by treatment, e.g. myelosuppression). Doppler ultrasound may document changes in hepatic portal

	venous flow and rule out alternative causes, but normal findings do not exclude sinusoidal obstruction syndrome. Grading: 1.mild: bilirubin <103 µM and weight gain <5%; 2.moderate: bilirubin 103-342 µM and/or weight gain ≥5% or ascites; 3.severe: bilirubin ≥342 µM and/or respiratory or renal failure or hepatic encephalopathy; 4. death due to SOS.
Thrombo-embolism	Venous and/or arterial TE. Confirmation by imaging or by autopsy is required for grade 2 and higher. Grading: 1. superficial thrombophlebitis or central venous line VL-associated deep venous thrombosis with neither symptom (e.g. pain, shortness of breath) nor objective signs (e.g. swelling, discolouration, collaterals); or causing only CVL dysfunction. Systemic anticoagulation not given, 2A. asymptomatic TE (including asymptomatic cerebral thrombosis). Systemic anticoagulation is usually given (not evidence-based), 2B. symptomatic DVT, systemic anticoagulation indicated, 3. symptomatic pulmonary embolism or cardiac mural thrombus without cardiovascular compromise or symptomatic cerebral sinovenous thrombosis or arterial ischaemic stroke; all grade 3 require systemic anticoagulation/antiaggregation. 4. life-threatening TE, including arterial insufficiency, haemodynamic or neurologic instability. Urgent intervention needed, 5. death due to TE.

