3.2 Secondary Objectives

- To assess the immunogenicity of eryaspase as determined by assessment of anti-L-asparaginase antibodies and neutralizing antibodies.
- To assess the overall safety and tolerability of eryaspase in combination with multi-agent NOPHO ALL 2008 chemotherapy according to the PdL toxicity consensus definitions for asparaginase related toxicities (hypersensitivity, pancreatitis, hyperlipidemia, SOS, thrombosis, osteonecrosis, and fungal infections)(25).
- Evaluate the effect of Eryaspase on the concurrent maintenance therapy with 6-mercaptopurine and methotrexate. Levels of cytotoxic methotrexate (MTX polyglutamates) and 6-mercaptopurine metabolites (6-thioguanine nucleotides, 6TGN, and methylated metabolites, MeMP) and of DNA-TGN levels in circulating leukocytes.

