4.2 Secondary Endpoints

The secondary endpoints are to evaluate:

- The safety and tolerability of eryaspase in combination with standard multi-agent NOPHO ALL 2008 or ALLTogether pilot protocol chemotherapy assessed during eryaspase treatment period according to potential toxicities defined in the Adverse Experience section.
- Toxicity of the eryaspase treatment compared to the conventional PEG-asparaginase treatment. Toxicity and SAE's will be evaluated according to the PdL toxicity consensus definitions.
- Levels of maintenance metabolites

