10.4 Serious Adverse Event Reporting

In addition to be recorded in patient's CRF, Serious Adverse Events and SUSARs will be recorded in a separate SAE form, and declared to the sponsor, whether attributed to the protocol or not. The

investigator is responsible for reporting the SAE's in accordance with the European Directive 2001/20/EC.

Therefore, a SAE report must be completed and faxed without delay and in any case within **24-hours of obtaining knowledge about the event to:**

[name] [name]
Children and Adolescent medicine
Aarhus University Hospital
[name]
[name], Denmark
Email: [contact] (email is preferable)
[contact]

If necessary, Investigator will be asked for additional information. SAE Follow-up report will be then completed and faxed to the sponsor in the same way as the initial report.

Any documentation regarding SAE, initial and follow-up report, should be archived together with patient's source documents.

The sponsor is responsible for immediately reporting all Unexpected Serious Adverse Reactions (treatment related events) to Competent Authorities and Erytech Pharma (and Ethical Committee(s) as needed), in accordance with the European Directive 2001/20/EC and mutual agreement between Erytech Pharma and the sponsor and the local requirements. Investigators will be informed as well.

The sponsor must ensure that all relevant information about suspected unexpected serious adverse reactions, which are fatal or life-threatening, is recorded and reported to the national competent authorities as soon as possible and no later than 7 days after the sponsor is informed of such a suspected adverse reaction. No later than 8 days after the reporting, the sponsor must inform the national competent authorities of relevant follow-up information on the sponsor's and the investigator's follow-up action to the reporting.

Any other suspected unexpected serious adverse reactions must be reported to the authorities no later than 15 days from the time when the sponsor is informed about them.

Furthermore, it is the sponsor's responsibility to prepare an annual safety reporting to national competent authorities and Ethics Committee.

Sponsor will keep detailed records of all adverse events which are reported to her by the investigator or investigators. These records shall be submitted to the Member States in whose territory the clinical trial is being conducted, if they request according to local regulations.

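### Fungal infection is a named safety outcome, but Protocol 10.2 also excludes hospitalised infections from reporting, so fungal cases may be under-counted to an unknown degree

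*Protocol*

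**What the plan says.** **The outcome.** The secondary safety objective (Protocol 3.2) lists the toxicities to be assessed under the cited consensus definitions: "hypersensitivity, pancreatitis, hyperlipidemia, SOS, thrombosis, osteonecrosis, and fungal infections". That is seven items. Section 10.2 repeats the list and says that safety "will be evaluated according to the PdL toxicity consensus definitions for asparaginase related toxicities". The secondary endpoints (4.2) assess safety "according to potential toxicities defined in the Adverse Experience section" and add "Toxicity of the eryaspase treatment compared to the conventional PEG-asparaginase treatment".

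**The exclusion.** Section 10.2 is headed as a list of events not to be reported and opens: "A number of toxicities are so well-known and frequent during therapy that they will not be reported". Its last bullet reads "Infection/fever leading to hospitalisation or prolongation of existing hospitalisation". Nothing is carved out for fungal infection, septic shock or death. The first bullet, on leukopenia and febrile neutropenia, is narrower and applies only "if the patient's condition otherwise is good with no signs of septic shock".

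**The definitions.** Table 3 has rows for hypersensitivity, silent inactivation, hyperlipidemia, osteonecrosis, pancreatitis, sinusoidal obstruction syndrome and thrombo-embolism. There is none for fungal infection.

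**The general rules.** Protocol 4.4 collects all AEs and SAEs up to 30 days after the last dose. Section 10.4 requires SAEs to be "declared to the sponsor, whether attributed to the protocol or not". SAP 8.1 has all AEs and SAEs entered in the eCRF and presented regardless of causality. The protocol synopsis, by contrast, collects only events potentially related to eryaspase. Section 10.0 first requires all AEs to be registered and then keeps unrelated events off the CRF.

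**The concern.** An investigator with a hospitalised patient who has a fungal infection finds two instructions in the same section. One makes the event part of the safety evaluation; the other puts hospitalised infection on the list of things not reported. An investigator who follows the exclusion leaves the event off the CRF. A reported case still has no definition or grade in Section 10, which is where 4.2 sends the reader.

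The error has a direction: non-reporting lowers the count and never raises it. A low fungal figure could then be read as good tolerability when it partly reflects the reporting rule. The same shortfall could carry into the comparison with PEG-asparaginase in 4.2, if the comparator events were collected without this exclusion. The documents do not say whether they were. The outcome is also a live one here, since Protocol 6.2 notes that antifungal prophylaxis is not recommended for the standard- and intermediate-risk patients in this study.

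**Working it through.** The plan states no figure for fungal infection, so there is nothing to reproduce. The check is mainly a comparison of passages, followed by an illustration of size.

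**Passages side by side**

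1. *Named toxicities against Table 3.* Of the seven named, six have a row; the seventh row of the table is silent inactivation. Fungal infection is the one named toxicity without a definition or grading. The table was read from a PDF, but it runs directly into 10.3 with no visible gap.
2. *Exclusion against objective.* The infection bullet covers any infection that causes or prolongs a hospital stay, and on its wording that includes fungal infection.
3. *Exclusion against its sibling.* The first bullet stops applying once there is septic shock. The infection bullet does not, so an infection with septic shock falls outside one waiver and inside the other.
4. *Exclusion against general rules.* Sections 4.4 and 10.4 and SAP 8.1 say collect all. Section 10.2 reads as the specific exception to them, and the relatedness limits in the synopsis and 10.0 act as a second filter. Section 10.2 also tells sites that such events reflect overall treatment intensity and not only asparaginase, which makes a judgement of unrelated more likely.
5. *Analysis.* The AE groupings in SAP 8.1 include no fungal or infection category, and the SAP cannot restore an event that was never entered.

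**Illustration of size**

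Let p be the true incidence, h the share of fungal infections that cause or prolong hospitalisation, and c the share of those still reported through the other rules. All three are assumptions; none is in the documents. N is 50 (Protocol 12.6) or 55 (SAP 4.1).

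- Reported incidence: R = p × [(1 − h) + h × c]
- Shortfall: p − R = p × h × (1 − c), which is never negative
- Expected reported cases: N × R
- Chance of no reported case: (1 − R)^N

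For p = 5% and N = 50:

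| h | c | R | Expected cases | Chance of none |
|---|---|---|---|---|
| any | 1 | 5.0% | 2.5 | 0.077 |
| 50% | 0.5 | 3.75% | 1.88 | 0.148 |
| 80% | 0.5 | 3.0% | 1.5 | 0.218 |
| 100% | 0.5 | 2.5% | 1.25 | 0.282 |
| 50% | 0 | 2.5% | 1.25 | 0.282 |
| 80% | 0 | 1.0% | 0.5 | 0.605 |
| 100% | 0 | 0% | 0 | 1 |

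Over p = 2% to 10%, full capture gives 50 × 0.02 = 1.0 to 50 × 0.10 = 5.0 expected cases (1.1 to 5.5 at N = 55). With strict exclusion (c = 0) and h between 50% and 100%, expected reported cases are 0 to 0.5 at p = 2% and 0 to 2.5 at p = 10%.

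Small numbers limit what any count can show. At p = 2% with full capture, the chance of no case is 0.98^50 = 0.364 (0.329 at N = 55).

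**The case against.** The best defence is that the documents keep several routes open. Sections 4.4 and 10.4 and SAP 8.1 ask for all events. SAEs also go to the NOPHO ALL 2008 or ALLTogether pilot toxicity registration. The 10.2 sentence that makes reporting mandatory follows both the list naming fungal infections and the mention of Table 3, so it can be read as covering them. The bullet itself may mean only that hospitalisation alone does not make an infection an SAE: hospitalisation is one seriousness criterion in 10.1, separate from death and threat to life, and three other bullets in the list speak of not being regarded as an SAE. The endpoint is secondary and descriptive, SAP 2.4.4 schedules no separate fungal rate, and the primary endpoint is untouched.

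Much of this stands, and it rules out stronger readings. A reader might infer that reported fungal incidence must come out near zero. That would need every case to be hospitalised and every site to apply the bullet without exception. A reader might infer that the cases are lost for good; the toxicity registration or source records may still hold them. A reader might also infer that septic reactions to the red-cell product go unnoticed, but 7.4.5 requires the investigator to be informed of any adverse reaction during the infusion or the hour after it.

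The defence does not remove the conflict. It relies on sites choosing the general rule over the specific one, or one reading of an ambiguous sentence over another. Under no reading does Section 10 supply a fungal definition.

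**Conclusion.** The inconsistency is real and worth correcting. One of seven named toxicities is both to be evaluated and, when it involves hospitalisation, on a list of events not reported; it also lacks a definition and grading. Fungal infections may therefore be under-ascertained to an unknown degree, and the reporting gap works only downward.

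The size cannot be derived from the documents. Under the assumed p of 2% to 10%, the shortfall at N = 50 runs from none (c = 1) to between 1 and 5 patients (h = 100%, c = 0). The upper end is a bound, not an expectation. An effect on the PEG-asparaginase comparison depends on how the comparator events were collected. The primary endpoint and its test are not affected.

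**What to change.** 1. **Protocol 10.2:** reconcile it with 3.2, 4.4 and 10.4 by stating that the infection bullet does not cover fungal infections, or infection with septic shock or death.
2. **Protocol Table 3:** add a fungal-infection row with definition and grading, taken from the consensus paper already cited, so that the mandatory-reporting sentence plainly covers all seven toxicities.
3. **SAP 8.1:** add a fungal category to the AE groupings.
4. **Patients already treated:** before database lock, check the NOPHO toxicity registration or source records for fungal infections, and state any remaining gap in the clinical study report. The documents do not say how completely the registration captures these events.

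Item 4 matters most. The SAP is dated May 2021 and enrolment was expected to finish by February 2020, so new protocol wording may reach few, if any, further patients. The cost is two wording changes, one table row, a few more SAE forms and a look-up for about 50 to 55 patients.
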